8.2. Subject Exclusion Criteria

The subjects who meet any of the following criteria will be excluded from the study:

- 1. Subject is at high risk of non-compliance in the opinion of the Investigator.
- 2. Subject plans to initiate treatment with a prohibited psychotropic medication during the study.
- 3. Subject plans to initiate treatment with transcranial magnetic stimulation (TMS), electroconvulsive therapy (ECT), vagus nerve stimulation (VNS), or deep brain stimulation (DBS) during the study.
- 4. Subject experienced a moderate or severe hyperprolactinemia-related AESI in the lead-in study of SEP-4199 CR.
- 5. Subject will require treatment with a drug that is associated with increases in QTc interval (see Section 23, Appendix IV for a list of medications, not all inclusive).
- 6. Subject had any of the following at Visit 6/EOT (Day 42) of the lead-in study of SEP-4199 CR based on machine reading:
 - increase in QTcF interval of ≥ 30 msec from Baseline of the lead-in study of SEP-4199 CR AND a QTcF interval ≥ 480 msec
 - increase in QTcF interval \geq 60 msec from Baseline of the lead-in study of SEP-4199 CR
 - QTcF interval > 500 msec
 - treatment-emergent clinically significant ECG abnormality.

- Subject is considered by the Investigator to be at imminent risk of suicide or injury to self or others, has a MADRS item 10 (suicidal ideation) score ≥ 4, or answers "yes" to "suicidal ideation" item 4 (active suicidal ideation with some intent to act, without specific plan) or item 5 (active suicidal ideation with specific plan and intent) on the C-SSRS assessment at Visit 6/EOT (Day 42) of the lead-in study of SEP-4199 CR.
- 8. Female subject of child-bearing potential has a positive urine pregnancy test at Visit 6/EOT (Day 42) of the lead-in study of SEP-4199 CR or plans to become pregnant during the current study.
- 9. Subject tests positive for any drug of abuse or cannabis at Visit 6/EOT (Day 42) of the lead-in study of SEP-4199 CR.

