12.1.3. Adverse Events of Special Interest

Adverse events of special interest (AESI) collected during the study will include all hyperprolactinemia-related events, regardless of seriousness. Hyperprolactinemia-related AESI include, but are not limited to the following:

- Galactorrhea/breast discharge
- Breast disorders including gynecomastia, pain, swelling (moderate or severe events only)
- Lack of or delayed menorrhea, or other menstrual disorders
- Fractures/osteoporosis/osteopenia
- Sexual dysfunction in females and males including erectile dysfunction/changes in libido
- Any estrogen-related laboratory abnormality
- Prolactin-producing pituitary tumor
- Hirsutism

Subjects should be instructed to notify the clinical site within 24 hours if they develop any of the signs or symptoms noted above.

Subjects who develop any of the following AESI: amenorrhea (missed menses for a minimum of 3 months), symptomatic gynecomastia, or galactorrhea that does not resolve within 2 weeks of temporary study drug interruption or that recurs with re-challenge must be discontinued from the study, referred to the Investigator for follow-up evaluation, and followed until the event resolves. Re-challenge will be at the Investigator's discretion (see Section 13.1).

For AESI, if the event meets seriousness criteria, the Investigator will report the event to the Sponsor within 24 hours of the site being made aware of the event, as outlined in Section 12.4.1. AESI that do not meet seriousness criteria will be reported by the Investigator to the Sponsor within 5 business days of site awareness and in the same manner that SAEs are reported.

12.2. **Objective Findings**

Clinically significant changes from signing of the ICF in objective findings (eg, clinical laboratory value, ECG value, vital signs, and physical or neurological examination observation), as determined by the Investigator, will also be recorded as AEs.

When a clear diagnosis is available that explains the objective findings, this diagnosis will be recorded as the AE, and not the abnormal objective finding (eg, viral hepatitis will be recorded as
the AE, not transaminase elevation). If a definite diagnosis is not available, then the sign (eg, clinically significant elevation of transaminase levels) or symptom (eg, abdominal pain) will be recorded as the AE.

Clinical laboratory test results and ECG tracings and over-read reports will be reviewed, signed, and dated by the Investigator.

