Any clinical laboratory value outside the normal range and any centrally over-read abnormal ECG finding will be flagged for the attention of the Investigator or appropriate designee at the study center. The Investigator or appropriate designee will indicate whether the value/finding is of clinical significance. Subjects with any clinically significant abnormal ECG finding at Visit 1E will be discontinued from the study (see Section 8.2). If a clinically significant laboratory or ECG abnormality is found after Visit 1E, during the study, and/or at the Follow-Up Visit, this should be recorded as an AE. Discontinuation due to AE with follow-up until resolution is mandatory for clinically significant ECG findings and hyperprolactinemia-related adverse events (see Section 13). Possibly drug-related or clinically relevant abnormal values of uncertain causality must be repeated. Additional laboratory and ECG testing during the study may be performed if medically indicated.

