13. TERMINATION OF SUBJECT FROM STUDY/DISCONTINUATION OF STUDY DRUG

13.1. Criteria for Subject Termination

Subjects may terminate the study participation at any time for any reason.

The possible reasons for the termination of study participation are as follows:

- Adverse event
- Lack of efficacy (specify)
- Lost to follow-up (specify)
- Pregnancy
- Withdrawal of consent (specify)
- Non-compliance with study drug (specify)
- Protocol deviation (specify)
- Death
- Other (specify)

If at any time during the course of the study, in the opinion of the Investigator, the subject may no longer safely participate due to a change in medical status (eg, experiences an AE, becomes pregnant), the subject must be discontinued from the study.

Discontinuation due to AE with follow-up until resolution is mandatory in the following cases:

- Subject who, at any study visit post-Baseline, has a QTcF interval > 500 msec, or who has a ≥ 60 msec increase in QTcF from Baseline (machine reading or centrally overread report), or who experiences a life-threatening cardiac arrhythmia must be discontinued from the study, referred to the Investigator for follow-up evaluation, and followed until the event resolves; in addition, an associated AE must be reported.
- Subject who develops an AE of amenorrhea (missed menses for a minimum of 3 months), symptomatic gynecomastia, or galactorrhea that does not resolve within 2 weeks of study drug interruption or that recurs with re-challenge must be discontinued from the study, referred to the Investigator for follow-up evaluation, and followed until the event resolves.
- Subject who answers "yes" to "suicidal ideation" item 4 (active suicidal ideation with some intent to act, without specific plan) or item 5 (active suicidal ideation with specific plan and intent) on any post-Baseline C-SSRS assessment must be discontinued from the study, referred to the Investigator for follow-up evaluation, and followed until the event resolves; in addition, an associated AE must be reported.
- Subjects who require hospitalization/prolonged hospitalization for treatment of COVID-19-related illness will be discontinued. Subjects with an active COVID-19 infection should be discussed on a case-by-case basis with the IQVIA Medical

Monitor to obtain agreement on whether a subject with an active COVID-19 infection should be discontinued.

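### Protocol 12.2 makes withdrawal mandatory for hyperprolactinemia-related adverse events without the limits that 13.1 and 12.1.3 set

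*Protocol*

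**What the plan says.** Four places in the protocol bear on what happens to a subject who develops a hyperprolactinemia-related event.

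- **12.2 Objective Findings:** "Discontinuation due to AE with follow-up until resolution is mandatory for clinically significant ECG findings and hyperprolactinemia-related adverse events (see Section 13". Apart from the reference to Section 13, nothing limits the prolactin part.
- **13.1 Criteria for Subject Termination:** the prolactin item names amenorrhea (at least 3 months of missed menses), then "symptomatic gynecomastia, or galactorrhea that does not resolve within 2 weeks of study drug interruption or that recurs with re-challenge must be discontinued".
- **12.1.3 Adverse Events of Special Interest:** the same limited rule, ending "galactorrhea that does not resolve within 2 weeks of temporary study drug interruption or that recurs with re-challenge must be discontinued from the study", with re-challenge left to the investigator. The AESI list in this section is much wider than the three named events and is not exhaustive. One entry is "Sexual dysfunction in females and males including erectile dysfunction/changes in libido".
- **10.1.1 Dose Adjustment Criteria:** a subject with a hyperprolactinemia-related AESI may not go up to 400 mg/day. For specific events of this kind the investigator may interrupt the drug temporarily, with a reference to 13.1.

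Discontinuation due to an AE is part of the primary objective (Protocol 5.1) and is listed among the primary endpoints (SAP 3.2.1).

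**The concern.** A mandatory stopping rule should read the same wherever it appears. Here a site that acts on 12.2 alone would withdraw a subject whom 13.1 and 12.1.3 do not require it to withdraw, and whom 10.1.1 would keep at 200 mg/day or interrupt and re-challenge.

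Two things are at stake. A subject could lose treatment without need. And sites could apply different rules to the same event, so that the AE discontinuation rate partly reflects which section a site followed. SAP 18.1.2 identifies these discontinuations from CRF fields (the AE marked as causing study discontinuation, the disposition reason, drug withdrawn). It has no step that separates a withdrawal required by 13.1 from one made on the broader words of 12.2.

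**Working it through.** The point concerns wording, and the plan gives no figure to reproduce. The check applies each rule to the same cases.

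| Event in the extension | 12.2 read literally | 13.1 and 12.1.3 | 10.1.1 |
|---|---|---|---|
| Galactorrhea that persists beyond 2 weeks of interruption, or recurs on re-challenge | Withdraw | Withdraw | Interruption came first |
| Galactorrhea that clears within 2 weeks and does not recur | Withdraw | Not required | Interruption allowed |
| Delayed menses, less than 3 months | Withdraw | Not required | No increase to 400 mg/day |
| Change in libido | Withdraw | Not required | No increase to 400 mg/day |

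1. **Direct conflict.** The second row is the firmest. Sections 13.1 and 12.1.3 describe a path of interruption, observation for 2 weeks and possible re-challenge, and 10.1.1 permits the interruption. If any hyperprolactinemia-related AE forces withdrawal, that path cannot be used.

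2. **Support from the dose rule.** The bar on up-titration in 10.1.1 applies to subjects with any such AESI. It would have little purpose if all of them had to leave the study.

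3. **Alternative grammar.** In 12.2 the words *clinically significant* might be read as covering the prolactin events as well as the ECG findings. The sentence would still lack the named events, the 3-month minimum and the interruption condition.

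4. **Ambiguity inside 13.1.** It is not clear whether the 2-week and re-challenge condition attaches to all three named events or to galactorrhea only. Section 12.2 is broader under either reading.

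5. **A route by which 12.2 could be applied.** Section 12.2 tells sites how to handle flagged laboratory results. Prolactin values after the first extension dose are not masked (Protocol 7.2) and are collected repeatedly (Table 2). An investigator who marks a raised value as clinically significant records it as an AE under 12.2. The next sentence of 12.2, taken literally, then requires withdrawal. Section 13.1 does not.

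**Scale.** The documents give no count of affected subjects, so no effect can be estimated. For orientation only: SAP 4.4 reports 64 enrolled. If all 64 were dosed (an assumption), one subject handled differently would move the overall AE discontinuation rate by 1/64 = 1.6 percentage points.

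**The case against.** **The pointer and the context.** The sentence in 12.2 refers to Section 13 and opens with the same words as the list there: "Discontinuation due to AE with follow-up until resolution is mandatory in the following cases". Section 13.1 is headed as the criteria for termination, 12.1.3 states the limited rule just before 12.2, and 10.1.1 also sends the reader to 13.1. A careful site would probably arrive at 13.1. This stands and lowers the risk, but it does not remove the inconsistency. A cross-reference does not narrow a sentence that says *mandatory*, and nothing states which section prevails.

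**The supporting arguments are inferences.** Exclusion criterion 4 reads "Subject experienced a moderate or severe hyperprolactinemia-related AESI in the lead-in study of SEP-4199 CR", so a mild lead-in event does not by itself bar entry. The up-titration bar could serve subjects who entered with such an event. Exclusion 4 also concerns entry rather than stopping, and the lead-in study's AESI definition is not in these documents. That is fair. The case therefore rests on the interruption and re-challenge path, with the dose rule and the entry rule as context only.

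**Investigator judgment.** Section 13.1 also requires discontinuation when, in the investigator's opinion, "the subject may no longer safely participate due to a change in medical status". A fracture or a pituitary tumor might lead to withdrawal by that route. The two sections therefore differ only for events that fall outside the named criteria and that the investigator considers safe to continue.

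**Timing.** The SAP, final on 25JAN2024, attributes its small sample to early termination. A protocol edit may have little conduct left to change.

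**The ECG half.** A reader might infer that the ECG wording in 12.2 is wrong in the same way, because 13.1 names only a subject who "has a QTcF interval > 500 msec, or who has a ≥ 60 msec increase in QTcF from Baseline" or who has a life-threatening arrhythmia. The documents do not support that. Exclusion 6 bars a treatment-emergent clinically significant ECG abnormality at entry, and 12.2 itself removes subjects with any clinically significant ECG finding at Visit 1E. The broader ECG wording is consistent with both and may be deliberate.

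**Conclusion.** The prolactin clause in 12.2 is wrong as written, and the error is minor. Read literally, it conflicts with 13.1, 12.1.3 and 10.1.1 on a mandatory stopping rule that feeds a primary endpoint. The likely intent is that 13.1 governs, but that is inferred from the pointer and the shared wording.

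The conclusion rests on the text alone. It assumes that a site could act on 12.2 without following its reference; no document shows that one did.

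Two stronger conclusions might be drawn and are not supported:

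- **That the AE discontinuation rate is distorted.** No affected subject is shown, no hypothesis is tested (Protocol 15.2, SAP 7.6), and no decision rule depends on the rate.
- **That the size of the problem can be read from the wording.** Counting the AESI entries that 13.1 does not name, or marking out a range of QTcF values between the dose-increase limits in 10.1.1 and the stopping limits in 13.1, describes text. Neither measures how many subjects were handled differently.

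**What to change.** In Protocol 12.2, change only the prolactin part of the sentence, to: *and for the hyperprolactinemia-related adverse events that meet the criteria in Section 13.1*. Leave the clinically significant ECG wording unchanged. Cutting it back to the QTcF and arrhythmia items in 13.1 would loosen a cardiac safety rule for a compound on which Protocol 4.3 reports QTc prolongation.

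The edit is one clause and needs no new data, visit or analysis. As a protocol revision it still needs written sponsor and IRB/IEC approval (Protocol 17.5).

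If conduct has ended, an amendment serves no purpose. The study report should then state that 13.1 governed, and withdrawals for hyperprolactinemia-related AEs should be checked against the 13.1 criteria. Any that fall outside should be identified beside the AE discontinuation table. With 64 enrolled, this is a short listing review.

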12.3. Collection and Recording of Adverse Events

All AEs must be recorded in the subject's study records/source documents in accordance with the Investigator's normal clinical practice. All AEs that occur from the signing of the informed consent to the subject's last visit must be recorded on the eCRF.

All AEs will be followed until resolution, stabilization of the condition, the event is otherwise explained, or the subject is lost to follow-up.

Each AE is to be evaluated for duration, severity, frequency, seriousness, action taken with the study treatment, outcome, and causal relationship to the study treatment. Definitions for severity, frequency, action taken with the study treatment, outcome, and causal relationship to the study treatment are presented below.

The severity of AE:

- **Mild** Ordinarily transient symptoms that do not influence performance of subject's daily activities. Other treatment is not ordinarily indicated.
- **Moderate** Marked symptoms sufficient to make the subject uncomfortable. Moderate influence on performance of subject's daily activities. Other treatment may be necessary.
- Severe Symptoms cause considerable discomfort. Substantial influence on subject's daily activities. May be unable to continue the study, and other treatment may be necessary.

The frequency of AE:

- **Once** an isolated episode
- Intermittent occurs on two or more separate occasions
- **Continuous** does not abate from date of onset to date of resolution

The action taken with the study treatment:

- **Drug Interrupted** Study drug stopped temporarily.
- Drug Withdrawn Study drug stopped permanently.
- Dose Reduced
- Dose Increased
- Dose Not Changed
- Not Applicable
- Unknown

The outcome of the AE:

- Recovered/Resolved
- Recovering/Resolving
- Not Recovered/Not Resolved
- Recovered/Resolved with Sequelae
- Fatal
- Unknown

The causal relationship of the AE to the study treatment: Not related

- **Not related -** Improbable temporal relationship and is plausibly related to other drugs or underlying disease.
- Related
 - **Possible** occurred in a reasonable time after study drug administration, but could be related to concurrent drugs or underlying disease.
 - **Probable** occurred in a reasonable time after study drug administration, is unlikely to be attributable to concurrent drugs or underlying disease, and there is a plausible mechanism to implicate the study drug.
 - **Definite** occurred in a reasonable time after study drug administration and cannot be explained by concurrent drugs or underlying disease. The adverse event should respond to dechallenge/rechallenge; however, this is not mandatory before assigning a definite causality.

The Medical Monitor is the initial contact person for protocol related questions or discussion of AEs. The contact information for the Medical Monitor as well as other emergency contact information can be found in Table 1 of this protocol.

12.4. Immediately Reportable Events

The following medical events must be immediately reported to the Sponsor:

• SAE

• Pregnancy

Additionally, AESI (defined in Section 12.1.3) that do not meet serious criteria must be reported to the Sponsor within 5 business days of the site's first awareness of the event.

Emergency contact information can be found in Table 1.

12.4.1. Serious Adverse Event

If the Investigator or study center staff becomes aware of an SAE that occurs in a study subject after first administration of study drug through 30 days following the last dose of the study drug, this must be reported immediately to the Sponsor whether considered related or unrelated to the study drug. SAEs that occur from the signing of the ICF up to the last visit must be recorded on the eCRF, and the data recorded should agree with those on the SAE form.

Should the Investigator become aware of an SAE greater than 30 days post last dose, the Investigator or an authorized delegate should report SAEs "spontaneously" to PPD-Pharmacovigilance (PVG) if considered at least possibly related to the study drug.

SAEs will be followed until resolution, loss to follow-up, stabilization of condition, or the event is otherwise explained.

An initial or follow-up SAE form as applicable must be completed and signed and sent via fax or email (see Table 1) to PPD-PVG immediately but no more than 24 hours after the Investigator or study center staff become aware of the event. The SAE form must be signed by the Investigator or appropriate designee. The Sponsor provides the SAE form used to report SAEs.

The Sponsor or designee will promptly notify all study centers and Investigators of an SAE that is determined to be expedited to the Regulatory Authorities in accordance with applicable law(s) and regulation(s). These SAEs must be promptly reported to the Institutional Review Board (IRB) or Independent Ethics Committee (IEC) by the Investigator or the appropriate person at the study center if required per IRB/IEC guidelines.

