11.5. Pharmacokinetic Assessments

Blood samples will be collected for population pharmacokinetics and plasma prolactin at the following visits: Visit 2E (Week 2/Day 14), Visit 4E (Month 2), Visit 6E (Month 4), Visit 8E (Month 6), Visit 10E (Month 8), Visit 12E (Month 10), Visit 14E (Month 12), and Follow-up (Visit 15E, 7 ± 2 days after last dose). See Section 22, Appendix III for sample collection and handling guidelines.

Prior to PK blood sample collection, subjects will record the date and time of their 3 most-recent study drug doses; the clinical site staff will record the dates and times of the 3 doses in the eCRF for each of the PK collection visits during the treatment period.

Plasma samples will be analyzed for concentrations of aramisulpride and esamisulpride using a validated enantioselective liquid chromatography-tandem mass spectrometry (LC-MS/MS) method. Plasma samples will also be analyzed for prolactin concentrations by an enzyme-linked immunosorbent assay (ELISA).

Remaining plasma samples after amisulpride PK and prolactin analysis may also be used for the additional bioanalytical method development and/or characterization of putative metabolites of amisulpride and for other exploratory measurements, if needed.

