12. SAFETY REPORTING

12.1. Definitions

12.1.1. Adverse Events

An adverse event (AE) is any untoward medical occurrence associated with the use of a drug in humans, whether or not considered drug related.

Untoward medical occurrences that occur after signing Study SEP380-303 ICF will be considered AEs.

An AE can, therefore, be any unfavorable and unintended sign (including an abnormal laboratory finding), symptom, or disease occurring after the administration of a medicinal (investigational) product, whether or not considered related to the medicinal (investigational) product. AEs may include the onset of new illness and the exacerbation of pre-existing conditions. AEs will be collected from the signing of the ICF to the last study visit (Follow-up Visit).

The Investigator should attempt to establish a diagnosis of the event based on signs, symptoms, and/or other clinical information. In such cases, the diagnosis should be documented as the AE and not the individual signs/symptoms.

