15.4.3.1. Adverse Events

All AEs will be coded using the Medical Dictionary for Regulatory Activities (MedDRA). Information on the format and version of the coding dictionary is provided in the DMP.

A treatment-emergent adverse event (TEAE) (hereafter referred to as AE) is an adverse event with onset data on or after the first day of the open-label treatment period through 7 days after study drug discontinuation (14 days for serious adverse events). The start of the open-label treatment period is defined as the first dose day for subjects previously randomized to placebo group and the OL Baseline visit date for subjects previously randomized to SEP-4199 CR groups.

The incidence of AEs, SAEs, and AEs leading to discontinuation due to AEs (or SAEs) will be summarized by analysis group (by presenting the number and percentage of subjects with one or more AEs in each category). The number and proportion of subjects with one or more AEs within a system organ class (SOC) and by preferred term (PT) will be presented by analysis group as well. The incidence of AEs (by preferred term, grouped by SOC) will also be summarized by severity, by the relationship to study medication, by the action taken regarding the study medication, as well as by the outcome. In addition, AEs will also be summarized by SOC, high-level term (HLT), and PT by presenting the number and percentage of subjects within each AE category.

The incidence of AESI, including but not limited to hyper-prolactinemia related AEs, will be summarized for overall and by gender as appropriate. For selected AESI, Kaplan-Meier curves will be plotted by analysis group for time to the earliest onsets. AEs associated with EPS will be summarized by analysis group.

Incidence of post-treatment adverse events (defined as an AE with a start date after the date of last dose of study drug through the last contact/visit in the follow-up period) will be summarized separately for subjects in the follow-up population.

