## 7.5. WINDOWING CONVENTIONS

No visit windowing will be performed during the analysis for this study. Data will be analyzed according

to the schedule outlined in the CSP. However, with the exception of SAE and PWC, any data collected beyond 7 days post the last OLE dose will be excluded from the efficacy and safety analyses unless otherwise specified; these data will be presented in data listings only.

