#### 18.1.3. SERIOUS ADVERSE EVENTS (INCLUDING ADVERSE EVENTS LEADING TO DEATH)

SAEs are those AEs recorded as "Serious" on the "Adverse Events" CRF form. AEs leading to death are those AEs with "Outcome" = "Fatal" on the "Adverse Events" CRF form.

SAEs (including AEs leading to death) will be summarized by SOC and PT. A listing of SAEs (including deaths) will be presented.

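### SAEs count as treatment-emergent for 14 days after the last dose, but eCRF recording is required only to a last visit on day 5 to 9, so part of the window behind a primary endpoint has no required data

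*Protocol*

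**What the plan says.** **Window.** Protocol 15.4.3.1 (and the synopsis) counts an event as treatment-emergent "through 7 days after study drug discontinuation (14 days for serious adverse events"). The longer period for SAEs is explicit.

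**Collection.** Protocol 12.1.1 states that "AEs will be collected from the signing of the ICF to the last study visit (Follow-up Visit"). Protocol 12.3 repeats the limit: "All AEs that occur from the signing of the informed consent to the subject's last visit must be recorded on the eCRF". Protocol 12.4.1 applies it to serious events: "SAEs that occur from the signing of the ICF up to the last visit must be recorded on the eCRF". Protocol 11.5 and 11.6.15 place that visit: "Follow-up (Visit 15E, 7 ± 2 days after last dose").

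**Safety reporting.** Protocol 12.4.1 also covers any SAE that the site learns of "after first administration of study drug through 30 days following the last dose of the study drug, this must be reported immediately to the Sponsor". This goes on an SAE form to pharmacovigilance. No text requires eCRF entry of an SAE that starts after the last visit.

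**Analysis.** SAP 18.1.3 begins "SAEs are those AEs recorded as" serious on the Adverse Events CRF form, and SAP 18.1 uses the SEP380-303 database. SAP 7.5 says that "with the exception of SAE and PWC, any data collected beyond 7 days post the last OLE dose will be excluded", so SAEs later than day 7 are meant to stay in. It sets no upper limit, and the 14-day rule appears nowhere in the SAP. SAP 4.7 lists the main changes from the protocol, and the SAE window is not among them. SAP 3.2.1 lists SAE incidence among the primary endpoints.

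**The concern.** Three post-dose horizons apply to the same events: the last visit (required eCRF recording), day 14 (treatment-emergent definition) and day 30 (reporting to the sponsor). The analysis draws on the source with the shortest required horizon, while the protocol's definition promises a longer one.

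A site that follows the recording rule exactly can report a day-11 SAE to pharmacovigilance and never enter it on the eCRF. The sponsor would know of the event, yet it would be missing from the study's SAE table. Whether it is counted would depend on site habit or on a reconciliation step that neither document describes. The SAP 18.1.1 tables of AEs starting after the last dose use the same data and inherit the gap. Withdrawal effects are a stated safety objective, so the days after stopping are not incidental to this study.

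**Working it through.** The plan gives no figure to reproduce. The check is date arithmetic plus an expected count.

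**Inputs from the documents**
- SAE window: 14 days after stopping (protocol 15.4.3.1).
- Last visit: day 5 to day 9 (7 ± 2; protocol 11.5, 11.6.15).
- Completer's treatment: 360 days (Visit 14E, protocol schedule of assessments).
- Subjects enrolled: 64 (SAP 4.4).

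**Assumptions**
- SAE rate of 0.05 to 0.30 per person-year, constant over time. The documents give no rate.
- All 64 subjects were dosed and attended Visit 15E on the same day.
- A subject treated for 30 days stands for an early stopper.

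**Formulas**
- Gap g = 14 − day of last visit.
- Share of the post-dose window = g / 14.
- Share of risk time = g / (days treated + 14): g / 374 for a completer, g / 44 for a subject treated for 30 days.
- Person-years in the gap = 64 × g / 365.25.
- Expected SAEs in the gap = person-years × rate.

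| Last visit | g (days) | g/14 | g/374 | g/44 | Person-years | Expected SAEs at 0.05 to 0.30 |
|---|---|---|---|---|---|---|
| Day 5 | 9 | 64% | 2.4% | 20% | 1.58 | 0.08 to 0.47 |
| Day 7 | 7 | 50% | 1.9% | 16% | 1.23 | 0.06 to 0.37 |
| Day 9 | 5 | 36% | 1.3% | 11% | 0.88 | 0.04 to 0.26 |

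The overall range is therefore 0.04 (64 × 5 / 365.25 × 0.05) to 0.47 (64 × 9 / 365.25 × 0.30) expected SAEs in days without required recording. If one such event were left out in a subject with no other SAE, incidence would change by 1/64 = 1.6 percentage points.

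The extreme for one subject is a last visit on the day of the last dose with Visit 15E missed: g = 14, the whole window. The protocol asks every subject to attend Visit 15E, so this would be an exception.

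With eCRF recording required through day 14, or through day 30 to match safety reporting, g falls to 0.

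**The case against.** A reader might infer that late SAEs are bound to fall out of the primary endpoint, or that the 14-day window cannot be filled. The documents do not support that. Protocol 12.4.1 sets a minimum for eCRF entry and does not bar later entry. SAP 7.5 exempts SAEs from the 7-day cut-off, and SAP 18.1 defines extension AEs by their start relative to the first open-label dose, with no end date. A late SAE that is entered will be counted. The open end could even admit an SAE starting after day 14.

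Other points that stand:

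- The 36% to 64% figures are shares of the post-dose tail, not of the time at risk, and not of SAEs.
- Visit 15E collects AEs and includes YMRS, C-SSRS and PWC. Events that began by then are captured and followed. Only onsets after that visit are at issue.
- SAP 4.7 lists main changes only, so its silence does not prove that the 14-day rule was kept.
- The pre-lock data review is described in a separate plan (SAP 2), which may include a reconciliation with the safety database.
- The study is uncontrolled and descriptive, and the expected number of events is below one half.

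What does not stand is the view that existing rules already close the gap. The requirement in protocol 12.4.1 that eCRF and SAE form agree belongs to the sentence about SAEs up to the last visit, so it does not reach later ones. A primary endpoint should not rest on optional entry by sites or on an unseen plan.

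**Conclusion.** The point holds as a gap in required capture, not as a certain loss of events. The protocol's treatment-emergent window for SAEs runs 5 to 9 days beyond the period for which eCRF recording is required, and the SAP names no other source for the SAE tables. Safety surveillance is not affected, because SAEs known to the site still reach the sponsor through day 30.

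The size is small: under half an expected event in 64 subjects. That figure rests on the assumed rate range and on a constant rate. It is also the number of SAEs expected in the gap, so the number actually missed is lower if sites enter some of them anyway. Because 64 is the number enrolled, it is an upper bound on the number dosed. The relative weight is greatest for subjects who stop early, which matters in a study cut short. Relative to the protocol's own window, the gap can only lower SAE incidence. The correction is cheap enough to be worth making.

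**What to change.** 1. Before database lock, reconcile the SEP380-303 clinical database against the safety database, and add every reported SAE with onset through last open-label dose + 14 days.
2. In SAP 7.5 and 18.1.3, state that SAE tables use onset through last open-label dose + 14 days. Alternatively, declare a different window and its data source in SAP 4.7.
3. If the protocol is still being amended, align the eCRF recording period in 12.4.1 with the chosen window. With enrolment finished and the study ended early, steps 1 and 2 carry most of the value.

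The cost is one reconciliation step and a few sentences, with no new visit. The SAE count may rise slightly. One limit remains: no contact is scheduled after Visit 15E, so ascertainment from then to day 14 depends on the site happening to learn of an event. The study report should say so.
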